2.3. A detailed description of four groups

Three groups in intervention cohorts will receive the same length of rehabilitation, i.e., 4 hours per day. Therapists in each group will be maximally helpful and will adopt a schedule for each patient to complete all the sessions. The treatment in each session will be led in person by well-educated, experienced therapists specially trained in each method. The treatment will be modified according to the patient's status and reaction to the therapy. Physical load during all therapies will be perceived maximally as a moderate level of intensity [12 - 14 on the Borg Scale (45)]. Information about the treatment will be recorded using codes of Public Health Insurance, Czech Republic (codes correspond to The Current Procedural Terminology code set system).

Group 1: COMprehensive Intensive REhabilitation Program after STROKE implementing the ICF concept (COMIRESTROKE – ICF)

This interventional arm suits the purposes of setting individual goals of the therapy which take account of the given situation of the rehabilitated person (46-48). The ICF system establishes a common health language to articulate human functioning across the lifespan and from individual to population health settings system (49, 50). On the individual level, functioning is considered as an interaction between a health condition and the contextual factors facilitating or acting as a barrier for functioning (51). Focusing on patient's quality of life and participation domain of the ICF applies a paradigm shift in neurorehabilitation research design (52). Engagement in valued activities was found to be significantly associated with subsequent improvement in emotional well-being (53).

Patients randomized to the GROUP 1 will undergo a multidimensional assessment, a functional profile will be created and the individual goals and intervention proposed and defined throughout the ICF framework. Clinical application can be rather arduous (54) and sharing of the feasibility experience is highly valued. This study arm design follows recommendations and

experience with implementation of the ICF model into clinical practice in rehabilitation in people after stroke (55).

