Limiting the burden of iterative processing the proposed battery of clinical examinations, questionnaires surveys and filling out the ICF core set documentation which is then used to compile "ICF Categorical Profile", this study proposes a direct linking of some clinical test results to the codes included in the Comprehensive ICF core set for stroke used (56). Linking of normal-range clinical examination results may ease the procedure. Linking will take place regarding specified items from the test battery: WHODAS 2.0 (57) NIHSS, mRS, MoCA (58), MAL (59), FIM, BBS (60), TUG, NHPT, ARAT, GSS, 3F test, MAST. Overlapping items will be further discussed.

The clinical assessment involves the following three steps: 1) description of patient's problems and resource; 2) setting of mutually agreed goals, based on the functional profile; 3) and determination of intervention targets. The interdisciplinary team together with the patient will use the functional profile to define in detail the overall goal and sub-goals, and to determine specific therapeutic interventions to achieve them (42). Participants in this group will undergo four hours of treatment per day (the same time as in the remaining two cohorts), but the time spent with each specialist will depend on the individually set goals. The "ICF Intervention Table" will be used to monitor and evaluate the work during individual targeted interventions and will also serves as a means of communication between the members of the interdisciplinary team. The team will meet weekly to provide feedback, evaluate the fulfilment of the set goals and to adjust therapeutic procedures so that the goals of the therapy are best met.

After the end of the intensive complex inpatient program COMIRESTROKE – ICF, as the continuum of care, participants will be referred and to a short-term outpatient rehabilitation programme.

Group 2 and 3

Participants will undergo COMprehensive Intensive REhabilitation Program after STROKE routinely offered at the Department of Rheumatology and Rehabilitation, Third Faculty of Medicine, Charles University and Thomayer University Hospital (39) three hours per day. In the program, the multidisciplinary team of practitioners from different clinical fields (physiotherapy, occupational therapy, clinical speech therapy and psychology) will be led by a medical doctor, a specialist in rehabilitation and physical medicine. Efforts of the different team members are parallel and discipline oriented.

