In addition, participants in these two groups will undergo one hour of physiotherapy per day. **Group 2:** COMprehensive Intensive REhabilitation Program after STROKE implementing technology-based physical PT (COMIRESTROKE – TECH) Participants will receive a technology-based PT that follows the principles of sensorimotor learning, i.e. repeated specific and targeted functions in different environments / conditions in order to strengthen the memory footprint and initiate structural changes in the CNS. According to the indication, participants will be offered one of the robotic systems using an exoskeleton (Gloreha, Erigo and Meditutor) or a therapy using a virtual environment (61, 62).

Group 3: COMprehensive Intensive REhabilitation Program after STROKE implementing neuroproprioceptive "facilitation and inhibition" physiotherapy (COMIRESTROKE – NEFI). Participants will receive an individual neuroproprioceptive "facilitation, inhibition" PT (Vojta reflex locomotion, Bobath concept), where appropriate stimuli in a suitable time sequence are combined with the aim to maintain optimal motor pathway function and ability control (63, 64). After finishing this intensive complex inpatient program COMIRESTROKE, participants will undergo standard/not directed treatment offered by the Czech Health Care system. Information

as to the health and social care the rehabilitant received after hospitalisation will be collected by phone call.

Group 4: A comparative group will undergo standardly provided care at department of neurology including face to face physiotherapy (bed mobility, transfers, gait, therapeutic exercises, positioning, education).

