2.8. Hypotheses

This clinical trial will test the following scientific hypotheses:

I. COMIRESTROKE under all three settings has a positive influence on all outcomes and higher effect than control group.

II. COMIRESTROKE - ICF will have the highest impact on primary outcomes (GAS, PROMIS, WHODAS 2.0) and on such secondary outcomes that were identified as treatment goals. Furthermore, we expect the highest impact on the primary outcomes in the follow-up (three and twelve months after finishing the rehabilitation).

III. COMIRESTROKE – NEFI will have the highest effect on the secondary outcomes, mainly on motor functions. Moreover, it will most significantly lead to the initiation of plastic and adaptive processes, assessed by the level of lncRNAs in the peripheral blood.

IV. The most important predictor of effective rehabilitation will be the level of disability at admission time; however, the content of the rehabilitation will have an impact on perceived, clinical, and physiological changes of the rehabilitant.

The exploratory goals of this clinical trial are as follows:

Goal I - Improvement patterns: Considering the high number of measured outcomes, for a deeper understanding of therapy efficacy with respect to patient and treatment characteristics, this clinical trial will aim to identify groups of patients with similar improvement patterns post therapy.

Goal II - Item-level analysis: To provide a deeper understanding of the differences in effectiveness between the three therapeutic approaches, this clinical trial will plan to explore item-level between-group differences in improvement.

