2.9. Measuring the effectiveness of rehabilitation

To test hypothesis I., i.e., a positive influence on all outcomes, the effect of therapy for each therapeutic group will be assessed separately by paired t-tests performed on pre-test and post-test scores. The Wilcoxon rank test will be used on data where normal distribution cannot be expected.

To test hypotheses II. and III, a comparison between therapeutic groups will be performed using two sample Student t-tests on differences between measurement time points (or Wilcoxon tests respectively for data, where normal distribution of the differences cannot be expected). For hypothesis II, the COMIRESTROKE - ICF group will be compared against the rest of the participants. For hypothesis III, the COMIRESTROKE - NEFI group will be compared against the rest of the participants. A one-sided alternative will be tested according to our hypotheses. We will also implement the one-way ANOVA test to jointly compare all three groups for prepost differences. In addition, a Tukey post-hoc comparison will be made to detect any further group differences beyond our hypotheses.

To assess the overall impact of rehabilitation and to compare effectiveness of different therapeutic approaches for Hypotheses I – III in more complex way, and to test for effect of other covariates in Hypothesis IV, a linear mixed effect model will be used with random patient effect fitted to longitudinal patient data. Measurement effect, group effect and their interaction, as well as effects of other covariates such as the level of disability in admission time will be tested by F test.

To address Goal I, correlations between changes in different examination scores will be evaluated using Pearson correlation coefficient and its nonparametric analogies. A cluster analysis will be performed to identify different phenotypes. This will allow the identification of different groups of patients in relation to the efficacy of the neuro-rehabilitation programs.

To address Goal II, for selected multi-item instruments, item-response theory (IRT) and generalized linear regression models will be used to study differential item functioning with respect to rehabilitation groups. Account will be taken for other respondent characteristics. Use will be made of differential item functioning in change (DIF-C) analysis (7) in order to detect between-group differences.

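### The one-sided test of Hypothesis III, NEFI against all other participants pooled, can succeed when NEFI only equals TECH, so it shows neither a method effect nor the highest effect

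*Combined protocol and SAP*

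**What the plan says.** Section 2.8, Hypothesis III, predicts that COMIRESTROKE – "NEFI will have the highest effect on the secondary outcomes, mainly on motor functions". It adds that NEFI will do most to start plastic and adaptive processes, as read from lncRNA levels.

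Section 2.9 tests this with "two sample Student t-tests on differences between measurement time points" (Wilcoxon where normality fails). The contrast is: "For hypothesis III, the COMIRESTROKE - NEFI group will be compared against the rest of the participants". On direction: "A one-sided alternative will be tested according to our hypotheses".

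The treatment schedules are in sections 2.1 and 2.3:

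- **All three COMIRESTROKE arms:** "Three groups in intervention cohorts will receive the same length of rehabilitation, i.e., 4 hours per day".
- **TECH and NEFI:** the routine three-hour programme, which includes physiotherapy among four disciplines. "In addition, participants in these two groups will undergo one hour of physiotherapy per day".
- **ICF:** the same four hours, but "the time spent with each specialist will depend on the individually set goals".
- **Group 4:** standard neurology-ward care including face-to-face physiotherapy, with no hours stated. Section 2.1 makes it the comparator for the intensified arms.

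Section 2.9 also plans a one-way ANOVA on three groups, a Tukey post-hoc step for differences outside the stated hypotheses, and a mixed model whose group and interaction terms are judged by F test. It names no NEFI v TECH contrast and no adjustment for physiotherapy time.

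**The concern.** A result in favour of NEFI would be read as evidence for the neuroproprioceptive method. The Introduction says evidence on different physiotherapy approaches is lacking. The Discussion expects the trial to confirm a finding on Vojta therapy and to compare it with technology-based and ICF-based rehabilitation.

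The designated contrast does not isolate the method. NEFI differs from Group 4 by an entire intensive programme, and from ICF by how four hours are divided among specialists. Only against TECH are the scheduled hours the same and the type of physiotherapy the planned difference. Hypothesis I itself predicts that all three intensive arms beat control. If that is true, pooling Group 4 into the comparator tilts the Hypothesis III test towards NEFI before any NEFI-specific effect exists.

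There is also a logical gap. Beating the average of three arms does not show that NEFI is better than each of them, which is what Hypothesis III asserts.

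**Working it through.** **Inputs from the documents.** Allocation 1:1:1:1 (section 2.2). Total 210 and 70 per group, with d = 0.5, α = .05 and power .80 (section 2.6). One-sided t-test of NEFI v the rest (section 2.9).

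**The plan's own figure.** The plan gives no error rate for this test. The nearest figure is 70 per group. For d = 0.5, two-sided α = .05 and power .80, the normal formula gives 63 per group and the exact t-test 64. Reaching 70 needs an allowance the plan does not state, for example 63/0.90 = 70. Also, 3 × 70 = 210, whereas four arms of 70 make 280. That mismatch is a separate matter. Here it only means showing two arm sizes: 52 (210/4 = 52.5) and 70.

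**Assumptions.** Outcomes are changes with SD 1 and no dropout. NEFI = TECH, so there is no method effect. ICF lies d_ICF below NEFI and Group 4 lies d_G4 below NEFI; a negative value means better than NEFI. The documents give neither shortfall, so a range is shown.

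**Formula.** The expected difference, NEFI minus rest, is

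D = (0 + d_ICF + d_G4)/3, with SE = √(1/n + 1/(3n)).

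The chance of a one-sided success is about Φ(D/SE − 1.645).

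**One case by hand** (ICF equal, Group 4 lower by 0.5): D = 0.5/3 = 0.167.

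- n = 52: SE = √(1/52 + 1/156) = 0.160; 0.167/0.160 = 1.04; Φ(1.04 − 1.645) = 0.27.
- n = 70: SE = √(1/70 + 1/210) = 0.138; 0.167/0.138 = 1.21; Φ(1.21 − 1.645) = 0.33.

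Simulation of the pooled t-test gives 26% and 32%. These are slightly lower because the spread between the pooled arms enlarges the SD of the rest.

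**Range by simulation, Group 4 in the rest:**

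| ICF v NEFI | Group 4 v NEFI | D | Success, 52 per arm | Success, 70 per arm |
|---|---|---|---|---|
| equal | equal | 0 | 5% | 5% |
| equal | 0.2 lower | 0.067 | 11% | 12% |
| equal | 0.5 lower | 0.167 | 26% | 32% |
| 0.2 lower | 0.5 lower | 0.233 | 41% | 51% |
| 0.5 lower | 0.5 lower | 0.333 | 65% | 77% |
| 0.2 better | 0.5 lower | 0.100 | 14% | 17% |
| 0.25 better | 0.25 lower | 0 | 5% | 5% |
| 0.5 better | 0.5 lower | 0 | 4% | 4% |

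**Group 4 left out of the rest** (D = d_ICF/2):

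| ICF v NEFI | Success, 52 per arm | Success, 70 per arm |
|---|---|---|
| equal | 5% | 5% |
| 0.2 lower | 14% | 17% |
| 0.5 lower | 42% | 51% |
| 0.2 better | about 1% | about 1% |

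NEFI v TECH stays at about 5% in every row, because it does not involve the other two arms.

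**The case against.** **The ICF direction is open.** Section 2.3 says only that ICF time follows the patient's goals. Every participant must have an arm or leg motor deficit (section 2.2), so motor goals, and as much or more physiotherapy than in NEFI, are quite possible. The physiotherapy share of the routine three hours is not given either, so no arm's total is known. This stands. A reader might infer that ICF patients get less physiotherapy and that the false-success rate is therefore 65% to 77%. The documents do not support that. Those figures put a four-hour programme level with ward care and are an extreme.

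**Group 4 may not belong to the rest.** Section 2.9 refers to therapeutic groups and to all three groups, although the literal wording of the contrast includes everyone. If Group 4 is out and ICF equals NEFI, the test holds its 5%. A reader might infer that leaving Group 4 out cannot help; that is true only if ICF does worse than NEFI.

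**The Group 4 gap is not one hour of physiotherapy.** A reader might put it down to the extra hour, or treat d = 0.5 as that hour's value. Neither follows. The gap is the whole intensive programme, and d = 0.5 in section 2.6 is a sample-size input tied to the Berg Balance Scale.

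**Other analyses would estimate NEFI v TECH.** The Tukey step could supply it, and the mixed model is offered for Hypotheses I to III. This softens the point without removing it. Tukey is reserved for differences beyond the hypotheses, the F tests are not directed at this pair, and neither is named as deciding Hypothesis III.

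**Hypothesis III names a programme arm, and ICF is an intended comparator.** This is fair, and it means NEFI v TECH alone cannot settle the highest-effect claim: NEFI could beat TECH and lose to ICF. The fix therefore needs every pair.

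**Conclusion.** The concern holds in this form: the designated test of Hypothesis III can succeed when NEFI merely equals TECH, and success would establish neither a method effect nor that NEFI has the highest effect. The second failing is one of logic and needs no assumption about dose.

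The size of the first depends on assumptions. With ICF equal to NEFI and Group 4 in the rest, a Group 4 deficit of 0.2 to 0.5 SD raises the false-success rate from 5% to between 11% and 26% at 52 per arm (12% to 32% at 70). An ICF shortfall raises it further. An ICF advantage lowers it, and can cancel the bias or, with Group 4 excluded, make the test conservative. Even then the result would turn on the content of the other programmes and not on the NEFI method.

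Sections 2.1 and 2.3 give opposite numbers to the TECH and NEFI groups and must be reconciled. Both arms have the same schedule, so the conclusion is unaffected.

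**What to change.** In section 2.9:

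1. Require NEFI v TECH for any statement about the neuroproprioceptive method.
2. Require NEFI to beat TECH, ICF and Group 4 separately before saying it has the highest effect. Because all three must succeed, this claim needs no further α adjustment across the three contrasts.
3. Keep NEFI v rest as a supportive comparison of whole programmes, and state whether Group 4 is in the rest.
4. Tabulate delivered physiotherapy time by arm from the insurance treatment codes already recorded (section 2.3). Describe NEFI v ICF and NEFI v Group 4 as programme differences.

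This takes revised wording and one table, with no new data or patients. The cost is precision. A pairwise contrast uses about 52 v 52 patients instead of 52 v 156. One-sided power at d = 0.5 is then about 0.81 (0.90 at 70 per arm).

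Requiring all three contrasts costs more. If NEFI is truly 0.5 SD better than each arm, joint power at 52 per arm is at most 0.81 and at least 1 − 3 × (1 − 0.813) = 0.44. At 70 per arm it lies between 1 − 3 × (1 − 0.903) = 0.71 and 0.90.

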Moreover, focus will be placed on the identification of novel biological molecules reflective of effective rehabilitation by molecular assessment. Long non-coding RNA (lncRNA) are defined as RNA transcripts >200 nucleotides with limited coding potential (26). They have been classified into anti-sense, intronic, large intergenic, promoter associated and UTRassociated lncRNAs (27). They are involved in vital cellular regulation (28) including genomic imprinting (29), epigenetic chromatin modification (30), transcriptional interference (31) and nuclear export (32). Importantly, IncRNAs determine nervous system development (33). A majority of lncRNA display specific expression within neuroanatomical regions (34). Many of these lncRNAs display genomic localizations in close proximity to known neurodevelopmental regulators (35). This has led to the general hypothesis that the expanded diversity in lncRNAs is pivotal to the higher order cognitive ability of humans. Long noncoding RNAs as promising therapeutics biomarkers in IS: LncRNAs regulate key factors involved in ischemic/reperfusion injury eg. calcium overload (Chen et al 2019). Excessive calcium accumulation results in the activation of calcium/calmodulin-dependent protein kinase II (CaMKII), a family of serine/threonine kinases involved in IS pathogenesis (36). CaMKII is controlled by lncRNA C2dat1. Elevated levels of lncRNA C2dat1 have been identified in both in vitro and in vivo models of IS (36). Studies showed that IS injury leads to increased glutamate release activating N-methyl-D-aspartate (NMDA) receptors which initiate cellular apoptosis (37). Overexpression of lncRNA GAS5 increased the apoptotic rate in neurons with its administration resulting in a greater area of cerebral infarction in animal models (38). It has been suggested that inhibition of the lncRNA GAS5 could potentially reduce apoptosis and infarct size in IS leading to improved neurological functioning. Evidence has pointed to IncRNA moderation of autophagy, angiogenesis and oxidative stress caused by IS. Exploring IncRNAs involved in such processes will assist in understanding the recovery networks induced by IS rehabilitation approaches.

2. Participants and methods

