Blood – Total RNA extraction		х	х	-	
cDNA synthesis					
lncRNA assessment (C2dat1 , GAS5 ,					
MALATI, PARTICLE, H19, MEG3)					

*Tests recommended by General Health Insurance (GHI), Czech Republic.

The qualitative data will be collected in semi-structured interviews with patients as well as clinical specialists with the aim of capturing an extended health evaluation. Specialists will have the possibility to look at the hospital information system, or search in the National Register of Paid Health Services. Data will be captured using an electronic Case Report Form (eCRF) (65).

The following data will be collected:

Demographic and anamnestic data including personal factors (sex, age, education, occupation, social relations, living situation), weight and height, laterality index (66), number of days after the stroke event, personality based on the NEO-Five Factor Inventory (NEO-FFI) (67), pre-stroke functional status based on modified Rankin Scale (68), cardiovascular risk factors (69), the degree of neurological impairment according to the National Institute of Health Stroke Scale (70) and disability with the Modified Rankin Scale (42), Bamford classification of IS based on the initial presenting symptoms and clinical signs (71) as well as pharmacotherapy.

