In future, rehabilitation strategies should consider molecular biomarkers as indicators of improvements in neurobiological principles that support repair or compensatory strategies that stimulate adaptive responses in people after stroke (115). The role of lncRNA e.g., *MALAT1, SNHG12, MEG3* and *H19*, in ameliorating IS brain injury has now been recognised (25). They are pivotal factors in neuronal repair processes and enhance neurogenesis. Nevertheless, there is a lack of human studies and clinical trials involving lncRNAs in IS treatment. The medical community has stressed the urgency of implementing studies that may clarify the clinical impact of lncRNAs in the specific context of IS given their promising involvement in nervous system recovery.

In conclusion, the proposed clinical trial will determine the effectiveness of various rehabilitation approaches via analysis of physical, emotional and biological readouts. Therefore, this clinical trial will offer an innovative approach and will provide new direct and biological evidence of the effect of implementing the ICF model into the rehabilitation therapeutic arena.

References

1. Yagi M. YH, Matsui H., Morita K., Fushimi K., Fujimoto M., Koyama T., Fujitani J. Impact of Rehabilitation on Outcomes in Patients With Ischemic Stroke: A Nationwide Retrospective Cohort Study in Japan. Stroke; a journal of cerebral circulation. 2017;48(3):740-6.

2. Bindawas S. M. VV, Moftah E. Improved functions and reduced length of stay after inpatient rehabilitation programs in older adults with stroke: A systematic review and meta-analysis of randomized controlled trials. NeuroRehabilitation. 2017;40(3):369-90.

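### The one-sided test of Hypothesis III is undefined for the lncRNA readouts: no direction is stated, and the rationale supports no common side for the six transcripts

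*Combined protocol and SAP*

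**What the plan says.** Section 2.9 names the test for Hypotheses II and III: "To test hypotheses II. and III, a comparison between therapeutic groups will be performed using two sample Student t-tests on differences between measurement time points", with a Wilcoxon test where the differences are not expected to be normal. For the third hypothesis the contrast is fixed: "For hypothesis III, the COMIRESTROKE - NEFI group will be compared against the rest of the participants". The sidedness rule follows: "A one-sided alternative will be tested according to our hypotheses". The side must therefore come from section 2.8.

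For the molecular part, section 2.8 says of NEFI that "it will most significantly lead to the initiation of plastic and adaptive processes, assessed by the level of lncRNAs in the peripheral blood". It names no transcript, no combined score, and neither a rise nor a fall.

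Table 2 in section 2.4 lists six transcripts: C2dat1, GAS5 and "MALATI, PARTICLE, H19, MEG3" (the first of these four is MALAT1). Section 2.5.3 describes the assay and classes it among the other pre-specified outcomes, below primary and secondary. It gives no favourable direction, although most of the clinical scales in section 2.5 carry one.

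Section 2.9 also plans a one-way ANOVA on pre-post differences with Tukey comparisons, and a linear mixed model with F tests of measurement, group and their interaction.

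**The concern.** A one-sided test needs a side, chosen before the data are seen. For the clinical scales the side can be read from section 2.5 together with Hypothesis III. For the lncRNAs it cannot, so someone has to supply it later. Two things can then go wrong with the named test. If the side follows the observed difference, the nominal 5% error doubles. If a side is fixed in advance but wrongly, the test cannot detect the effect that is really there. The Discussion says the trial will provide biological evidence about rehabilitation, and such evidence needs a decision rule that can be applied as written.

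**Working it through.** **1. Is a direction stated or implied?** The rationale, transcript by transcript:

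| Transcript | What the documents say | Side implied |
|---|---|---|
| GAS5 | Introduction: "Overexpression of lncRNA GAS5 increased the apoptotic rate in neurons"; also "inhibition of the lncRNA GAS5 could potentially reduce apoptosis and infarct size in IS leading to improved neurological functioning" | lower |
| MALAT1, MEG3, H19 | Discussion: a role "in ameliorating IS brain injury has now been recognised"; described as repair factors | higher |
| C2dat1 | Introduction: raised in stroke models | none stated |
| PARTICLE | in the Table 2 panel; no stroke-related direction given | none stated |

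The GAS5 text concerns neurons and animal models, and the Discussion text concerns brain injury. The endpoint is the level in peripheral blood, and no section says which direction in blood is favourable for any transcript. No single side fits all six.

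**2. Inputs for the size of the effect.** Section 2.6 gives d = 0.5, α = .05, power .80, and 70 per group (210 in total). The d comes from the Berg Balance Scale, so using it for lncRNA is an assumption.

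The stated inputs do not reproduce 70. With n = 2(z_α + z_β)²/d², the two-sided result is 2(1.960 + 0.842)²/0.25 ≈ 63 and the one-sided result is 2(1.645 + 0.842)²/0.25 ≈ 50. A 10% dropout, which the documents do not state, would give 63/0.9 = 70. This point does not depend on that figure.

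Section 2.2 allocates 1:1:1:1 to four arms, so 210 patients give 210/4 = 52.5 per arm, whereas 70 per arm would need 280. The size of the comparison group is therefore unclear, and a range is used.

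**3. Power of NEFI against the rest at d = 0.5.** The non-centrality is δ = d·√(n₁n₂/(n₁+n₂)). For 52 v 158, δ = 0.5·√(52 × 158/210) = 3.13. By normal approximation:
- one-sided, right side: P(Z > 1.645 − 3.13) = 0.93
- one-sided, wrong side: P(Z > 1.645 + 3.13) ≈ 0.000001
- two-sided: P(Z > 1.960 − 3.13) = 0.88

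The non-central t gives:

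| NEFI v rest | One-sided, right side | One-sided, wrong side | Two-sided |
|---|---|---|---|
| 52 v 158 (210 over four arms) | 0.930 | 0.000001 | 0.876 |
| 52 v 105 (same, without the control arm) | 0.902 | 0.000002 | 0.834 |
| 70 v 140 (three arms of 70) | 0.961 | below 0.00001 | 0.925 |
| 70 v 210 (four arms of 70) | 0.976 | below 0.00001 | 0.951 |

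At d = 0.3 the ranges over the four splits are 0.55 to 0.70 on the right side, 0.0001 to 0.0003 on the wrong side, and 0.42 to 0.58 two-sided.

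**4. Error if the side follows the data.** Per transcript it is 0.05 + 0.05 = 0.10. Over six transcripts, assumed independent, the chance of at least one false positive is 1 − 0.90⁶ = 0.47, against 1 − 0.95⁶ = 0.26 with sides fixed in advance. The 0.26 is ordinary multiplicity. Only the step from 0.26 to 0.47 comes from the missing side.

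**The case against.** The strongest reply is that section 2.9 does not rely on the one-sided test alone. The mixed model is planned for Hypotheses I to III and its F tests have no direction; nor do the ANOVA and Tukey comparisons. This stands. A reader might infer that a fall in GAS5 could never be declared, or that the molecular hypothesis has no valid test. The documents do not support either, because these analyses could show a change both ways. They do not close the gap, however. The F test of the interaction is omnibus, not NEFI against the rest. The ANOVA is described for three groups in a four-arm trial. Tukey is assigned to differences outside the stated hypotheses. Nothing says which analysis decides Hypothesis III.

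A reader might also infer that the plan would count a harmful rise in GAS5 as success. No section says that higher is better for all six; the Introduction points the other way for GAS5, and even that is not a statement about blood levels. Nor does any section propose choosing the side after the data. The fault is silence, not a planned wrong-way test.

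It is also fair that the lncRNAs rank below the primary and secondary outcomes, and that Hypotheses I (all outcomes) and IV (physiological changes) touch on molecular change too. Hypothesis III is the one that names lncRNAs, but it is not the trial's only route to a molecular finding.

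**Conclusion.** The point holds for the named NEFI-versus-rest test of the lncRNA readouts. Its one-sided alternative is undefined, because section 2.8 states no direction and the rationale supports no common one. The size is conditional. A side chosen after the data gives an error of 0.10 per transcript instead of 0.05. A side fixed the wrong way gives power below 0.00001 at d = 0.5, where a two-sided test has 0.83 to 0.95 over the splits considered. These powers rest on an effect size borrowed from the Berg Balance Scale and on assumed arm sizes; the doubling of the error rests on neither. The primary outcomes and the clinical conclusions are unaffected, and this point does not question one-sided testing of the clinical scales.

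**What to change.** In section 2.9, exempt the lncRNA readouts from the one-sided rule. Test each of the six transcripts in Table 2 two-sided at .05, NEFI against the rest, and say that these tests decide the molecular clause. Extend the Benjamini-Hochberg correction expressly across the six; at present it is named only in section 2.7, beside the baseline comparisons. In section 2.8, reword the clause so that NEFI is expected to show a different change in expression from the other arms.

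Fixing a side for each transcript in advance would also define the test, but the documents support one for only some of the six and for none in blood, so two-sided testing is cleaner.

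The change is to wording only, with no extra samples or assays. Where a pre-guessed side would have been right, power at d = 0.5 falls by about 5 points with 52 v 158 (0.93 to 0.88), and from 0.96–0.98 to 0.93–0.95 with 70 per group. It falls by about 7 points with 52 v 105 (0.90 to 0.83). At d = 0.3 the loss is about 12 to 13 points (for example 0.589 to 0.463 with 52 v 158). The multiplicity correction costs some further power, not quantified here.
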